**Multicenter double-blind placebo-controlled parallel group
randomized clinical trial of efficacy and safety of MMH-407 in the
treatment of acute respiratory viral infection**

Phase III

Sponsor	ООО «NPF «MATERIA MEDICA HOLDING»
Protocol number	MMH-407-001
Version date:	July 01, 2019
ClinicalTrials.gov Id:	NCT04244084

Protocol Summary

This document represents the protocol summary for the study on human patients. The study will be carried out in accordance with ICH GCP, National Standard of the Russian Federation GOST 52379-2005 "Good Clinical Practice", Helsinki Declaration of World Medical Association, relevant requirements of the regulatory authorities as well as the study procedures.

Title of Study

Multicenter double-blind placebo-controlled parallel group randomized clinical trial of efficacy and safety of MMH-407 in the treatment of acute respiratory viral infection.

Phase: III

Sponsor: OOO "NPF "MATERIA MEDICA HOLDING", Moscow, Russia

Protocol No. MMH-407-001

Objective of the study

- To evaluate the efficacy and safety of MMH-407 in the treatment of acute respiratory viral infection (ARVI).

Endpoints

Primary endpoint

1. Time to resolution of ARVI symptoms^{1,2} (PCR-confirmed).

Secondary endpoints

1. Severity of ARVI (clinically diagnosed and/or PCR-confirmed); based on the area under the curve (AUC) data for the Total Severity (TS) score³ on days 1-6 of the observation).
2. Percentage of patients with resolution of ARVI symptoms (clinically diagnosed and/or PCR-confirmed).
3. Time to resolution of ARVI symptoms (clinically diagnosed and/or PCR-confirmed).
4. Percentage of patients with resolution of ARVI symptoms (PCR-confirmed).
5. Dosing frequency of antipyretics on days 1-3 of therapy⁴.
6. Percentage of patients requiring administration of antibiotics or hospitalization on 4-14 days of the observation.

¹ Time from enrollment to symptom resolution. **Resolution of ARVI symptoms** is defined if body temperature $\leq 37.30^{\circ}\text{C}$ within 24 hours (without further increase during observation period) + absence/presence of ARVI symptoms ≤ 2 .

² Based on a patient diary.

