Patient will be observed for 14 days (screening, randomization - Day 1, treatment period – 5 days, follow-up – up to 2 days; deferred “phone visit” – Day 14).

During the treatment and follow-up period the patients or investigators will make 3 visits and the fourth “phone visit” will be scheduled additionally: 1) visits by physician/patient - on Days 1, 5 and 7 (Visits 1, 2 and 3) – in a study center or at home; 2) “phone visit” (Visit 4) – on Day 14.

At Visits 2 and 3, the investigator will perform an objective examination, document changes in the symptoms and concomitant medications to check patient diaries. At Visit 3 compliance will be evaluated and laboratory tests will be performed. “Phone visit” is carried out to interview the

patient about his/her condition, presence/absence of secondary bacterial/viral complications and use of antibiotics.

During the study, symptomatic therapy and therapy for their co-morbidities are allowed with the exception of the drugs indicated in the section “Prohibited Concomitant Treatment”.

Inclusion and exclusion criteria

Inclusion criteria

1. Patients of either gender aged 18-70 years.
2. Diagnosis of ARVI based on medical examination: axillary temperature $\geq 38.0^{\circ}\text{C}$ at examination + total general symptoms score ≥ 4 , nasal/throat/chest symptoms score ≥ 2 .
3. The first 24 hours after ARVI onset⁵.
4. Patients giving their consent to use reliable contraception during the study.
5. Signed patient information sheet (informed consent form).

Exclusion criteria

1. Clinical symptoms of severe influenza/ARVI⁶ requiring hospitalization.
2. Suspected pneumonia, bacterial infection (including otitis media, sinusitis, urinary tract infection, meningitis, sepsis, etc.) requiring administration of antibiotics from the first day of illness.
3. Suspected initial manifestations of diseases with symptoms similar to ARVI at onset (other infectious diseases, flu-like syndrome at the onset of systemic connective tissue diseases, and other pathology).
4. Patients requiring antiviral medication prohibited within the study.
5. Medical history of primary and secondary immunodeficiency.
6. Medical history/suspicion of oncology of any localization (except for benign neoplasms).
7. Aggravation or decompensation of chronic diseases affecting a patient's ability to participate in the clinical trial.
8. Malabsorption syndrome, including congenital or acquired lactase or other disaccharidase deficiency, galactosemia.

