9. Allergy/ hypersensitivity to any component of the study drug.
10. Pregnancy, breast-feeding; childbirth less than 3 months prior to the inclusion in the trial, unwillingness to use contraceptive methods during the trial.

⁵ **Time of ARVI onset** is the time of manifestation of fever or febrile illness (axillary temperature $\geq 37.4^{\circ}\text{C}$, oral or tympanic temperature $\geq 37.6^{\circ}\text{C}$, or rectal temperature $\geq 38.0^{\circ}\text{C}$)

⁶ **Severe influenza/ARVI** [7] is characterized with abrupt onset, high temperature ($> 40^{\circ}\text{C}$) with acute intoxication symptoms (strong headache, body ache, insomnia, delirium, anorexia, nausea, vomiting, meningeal symptoms, sometimes encephalitic syndrome); pulse > 120 bpm, weak, sometimes arrhythmia; systolic blood pressure < 90 mm Hg; muffled heart sounds; respiration rate $> 28/\text{min}$. Very severe disease is characterized with fulminant presentation, rapidly developing intoxication signs, potential DIC-syndrome.

11. Course administration of the drug products specified in the section “Prohibited Concomitant Therapy” within two weeks prior to inclusion in the study.
12. Patients who will not fulfill the requirements during the study or follow the order of administration of the studied drug products, from the Investigator's point of view.
13. Medical history of mental diseases, alcoholism or drug abuse that according to the investigator's opinion will compromise compliance with the study procedures.
14. Participation in other clinical trials for 3 months prior to enrollment in this study.
15. Patients who are related to any of the on-site research personnel directly involved in the study or are an immediate relative of the investigator. ‘Immediate relative’ means husband, wife, parent, son, daughter, brother, or sister (regardless of whether they are natural or adopted).
16. Patients who work for OOO “NPF “MATERIA MEDICA HOLDING” (i.e. the company's employees, temporary contract workers, designated officials responsible for carrying out the research or any immediate relatives of the aforementioned).

Criteria for Withdrawal or Termination

1. Patient failed screening procedure.
2. Inability or refusal of patient to comply the Protocol requirements.
3. Deviation from the schedule of visits 2 and 3 for more than 1 day.
4. Necessity in medicines prohibited within the study.
5. An adverse event requiring the study drug cancellation.

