6. Desire of patient to complete the study ahead of schedule due to inefficacy of therapy or any other reason.
7. Pregnancy.
8. Cases not specified by the protocol where the investigator decides that further participation may harm the patient.
9. Incorrect inclusion of ineligible patient.

Number of patients

It is planned to include 240 patients (120 patients in MMH-407 and Placebo groups).

Interim analysis

The protocol does not schedule unblinded interim analyses. At the sponsor's decision blinded interim analysis may be carried out to specify population parameters and potential further specification of sample size (increase only).

Treatment

Group 1

Name of the medicinal product: MMH-407

Active ingredient: affinity purified antibodies to human interferon gamma – 10000 UMA*, affinity purified antibodies to CD4 – 10000 UMA*, affinity purified antibodies to β 1-domain of MHC class II – 10000 UMA*, affinity purified antibodies to β 2-microglobulin of MHC class I – 10000 UMA*

* *Units of the Modifying Activity.*

Excipients: Lactose monohydrate – 0.267 g, microcrystalline cellulose – 0.03 g, magnesium stearate – 0.003 g.

Method of administration: Tablet for oral use. One tablet per intake. On day 1, five tablets are taken in the first 2 hours (one tablet every 30 min), followed by three more tablets regularly spaced during the rest of the day. From day 2 through 5, one tablet is administered three times daily. The drug is administered not during meals (i.e. between the meals or 15-30 minutes before meal). The tablet should be held in mouth until complete dissolution.

Dosage form: Tablet for oral use.

Description: Flat, cylinder-shaped, scored beveled edge, white to off-white tablets.

Storage conditions: At temperature below 25°C. Keep out of the reach of children.

Group 2

Name of the medicinal product: Placebo

Active ingredient: NA

Excipients: Lactose monohydrate – 0.267 g, microcrystalline cellulose – 0.03 g, magnesium stearate – 0.003 g.

Method of administration: Placebo using MMH-407 scheme.

Dosage form: Tablet for oral use.

Description: Flat, cylinder-shaped, scored beveled edge, white to off-white tablets.

Storage conditions: At temperature below 25°C. Keep out of the reach of children.

Treatment duration

MMH-407/Placebo treatment duration is 5 days.

Observation period

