7. Combination preparations for symptomatic therapy of acute respiratory infections.
8. Homeopathic preparations.
9. Systemic (oral or parenteral) corticosteroids.
10. Immunosuppressants (L04).
11. Antineoplastic agents (L01) and combined (with hormones) antineoplastic endocrine therapy (L02).
12. Immune sera and immunoglobulins (J06).
13. Vaccines (J07).
14. Drugs that previously caused hypersensitivity/ allergic reactions in patient.

* Patients were allowed to take a single dose of prohibited medications (except for 9 - 14) prior to inclusion, if the interval between the medication intake and randomization was more than 12 hours.

Study design scheme

Schedule of study procedures

Procedure/Visit	Visit 1 (Day 1)	Visit 2 (Day 5)	Visit 3 (Day 7±1)	Visit 4 (Day 14±1)
-----------------	--------------------	--------------------	----------------------	-----------------------

Informed consent	+			
Registration of a study patient in the IVRS and assignment of patient ID	+			
Collection of complaints	+	+	+	
Medical history	+			
Physical examination	+	+	+	
ARVI symptoms registration	+	+	+	
Patient Diary	+	+	+	+
Pregnancy test	+			
Concomitant therapy	+	+	+	
Eligibility assessment	+			
Nasopharyngeal swabs for PCR	+			
Laboratory tests* (safety evaluation)	+		+	
Randomization	+			
Study drug supply	+			
Study drug accountability and return			+	
Treatment compliance			+	
Evaluation of treatment safety	+	+	+	
Visit completion	+	+	+	
Phone survey				+
Study completion**				+

* Including hematology, urinalysis, biochemistry (total protein, glucose, total bilirubin, creatinine, ALT, AST, cholesterol).

**In case of early withdrawal the procedure may be performed at visits 1, 2 or 3.

Statistical Analyses

SAS 9.4 will be used for data processing and statistical calculations.⁷

Samples

Total set: all patients who have signed ICF. This sample will consider all the recorded AEs, including those occurred prior to the study therapy.

Safety population: all patients who received at least one dose of the study drug. This sample will be used for ***analysis of the study treatment safety and tolerability***, as all adverse events identified after the study drug administration will be recorded.

Full Analysis Set. This sample includes all enrolled patients, except for those who met at least one of the following events:

- 1) non-compliance with inclusion / exclusion criteria;
- 2) the patient did not take a single dose of the study drug;

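### The withdrawal list puts stopping study drug, needing a prohibited medicine and missing a visit window beside leaving the study, and the supplied text provides no diary or Day 14 contact afterwards

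*Combined protocol and SAP*

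**What the plan says.** The document describes its own scope: "This document represents the protocol summary for the study on human patients". Everything here concerns that text only.

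The section Criteria for Withdrawal or Termination is one undivided list. Three of its items are not in themselves reasons to stop observing a patient:

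- item 3: "Deviation from the schedule of visits 2 and 3 for more than 1 day"
- item 4: "Necessity in medicines prohibited within the study"
- item 5: "An adverse event requiring the study drug cancellation"

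They stand beside items that plainly mean leaving the study, such as failed screening and item 6: "Desire of patient to complete the study ahead of schedule due to inefficacy of therapy or any other reason".

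In the Schedule of study procedures, study completion falls at Visit 4 (Day 14), with this footnote: "In case of early withdrawal the procedure may be performed at visits 1, 2 or 3". No section describes diary entries, visits or the Day 14 call after withdrawal.

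The primary endpoint comes from the patient diary. Its definition of resolution (Endpoints, footnote 1) also requires that temperature does not rise again during observation. Secondary endpoint 6 counts antibiotic use or hospitalization over Days 4–14. The Full Analysis Set drops ineligible patients, undosed patients and those with no post-dose data, so it keeps the partial data of other leavers.

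**The concern.** Stopping study drug and ending observation are different events, and the list does not separate them. If a site closes the record when item 3, 4 or 5 is met, three kinds of data can go missing although the patient might have supplied them: a resolution time not yet reached, confirmation that temperature did not rise again, and Day 4–14 events for endpoint 6.

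For items 4 and 5 the loss is plausibly related to outcome, since a patient who needs another medicine or has a drug-stopping adverse event may be recovering slowly. The same may hold for item 6 leavers citing inefficacy, but they are choosing to leave and can be followed only with their consent. Item 3 is administrative.

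Membership of the Full Analysis Set does not restore outcomes that were never collected, and censoring at withdrawal is unsafe when the reason for leaving is linked to recovery.

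**Working it through.** **The plan's own figures.** Inputs from Evaluation of sample size: SD 1.38 days, two-sided α 0.05, power 80%, 120 evaluable patients (60 per arm), withdrawal coefficient 0.5.

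- Detectable difference = (1.960 + 0.842) × 1.38 × √(2/60) = 0.706 day; the plan states 0.71.
- Footnote 12: 1 − 0.90 × 0.56 = 0.496, which matches 0.5, and 120/0.5 = 240.

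No stated figure is in dispute.

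**Assumptions not in the documents.** Withdrawal after randomisation of w = 5–10%. The plan's 10% also contains screening failures, so it is neither a forecast nor a ceiling. Time to resolution T follows the plan's N(5.17, 1.38), which it gives for the study-drug group. Visit 2 (Day 5) is elapsed time 4 or 5, depending on whether Day 1 counts as time 0 or time 1.

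**Patients without a resolution time.** PCR-confirmed leavers per arm = 120 × 0.56 × w = 3.36 (5%) or 6.72 (10%). P(T>4) = 0.802, P(T>5) = 0.549, P(T>2) = 0.989.

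| Scenario, per arm | w = 5% | w = 10% |
|---|---|---|
| Leave at Visit 2, diary planned to Day 14 (× 0.549 to 0.802) | 1.8–2.7 | 3.7–5.4 |
| Leave about time 2, before Visit 2 (× 0.989) | 3.3 | 6.6 |
| Leave at Visit 2, diary planned only to Visit 3 (× 0.457 to 0.528) | 1.5–1.8 | 3.1–3.5 |

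The last row removes patients who would be unresolved at Visit 3 anyway: 0.549 − 0.092 and 0.802 − 0.274. At w = 2% the first row is 0.7–1.1. With placebo shifted by 0.71 day (assumed), P(T>5) = 0.738 and P(T>4) = 0.913, so the first row is 2.5–6.1 over w = 5–10%.

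**Item 3 alone.** A late Visit 2 breaches the limit at Day 7, when P(T>7) = 0.092 to P(T>6) = 0.274 are unresolved. A late Visit 3 breaches it at Day 9, when at most P(T>8) = 0.020 are. Most diary information already exists by then, so what is lost is mainly the Day 14 contact. A visit held too early would breach sooner.

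**Bias in complete-case means** (the plan's hypotheses are on means). If a share L of an arm is lost with T > c, the observed mean is (m − L × E[T|T>c])/(1 − L). For c = 5, E[T|T>5] = 5.17 + 1.38 × 0.396/0.549 = 6.165.

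- 5% vs 10% lost, all unresolved: (5.17 − 0.05 × 6.165)/0.95 = 5.1176 and (5.17 − 0.10 × 6.165)/0.90 = 5.0594, a spurious 0.058 day. With c = 4: 0.028.
- 5% vs 10%, leaving unrelated to T: 0.022 (c = 4) or 0.030 (c = 5).
- 5% vs 10%, leavers exactly the slowest: 0.269 − 0.150 = 0.12 day.
- Equal rates and equal distributions: 0.
- Equal rates of 5–10%, true difference 0.71: observed about 0.72–0.75, an overstatement of 0.01–0.04 day.

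**Endpoint 6.** If leavers are kept as event-free and all their events follow withdrawal, the share of events missed is w × RR/((1 − w) + w × RR): 5–10% at RR = 1, 14–25% at an assumed RR = 3, and half of that if half the events come earlier. If leavers drop out of the denominator, the understatement is 1 − 1/((1 − w) + w × RR): 0 at RR = 1, 9–17% at RR = 3. The plan gives no base rate, so no absolute effect follows.

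**The case against.** The strongest objection is that this argues from silence in a summary. A fuller protocol may contain follow-up rules. The heading covers withdrawal or termination without saying from what, item 5 speaks only of the drug, and the schedule footnote is permissive. This stands as a limit: a reader might infer that the plan orders data collection to stop, but no sentence says so. Study exit remains the natural reading, because the items share a list with plain exits and study completion can be brought forward.

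A reader might also infer a serious bias in the primary result. The figures do not support that. In complete-case means it is nil to 0.06 day in most scenarios, and reaching 0.12 requires leavers to be exactly the slowest patients. Nor does unequal withdrawal have to be present: equal rates with a true difference give a small distortion too. Power is hardly touched. At 10% lost, 60.5 PCR-confirmed patients per arm remain and the detectable difference is 0.703 day; with none lost, 67.2 remain and it is 0.667.

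A third tempting inference is that antibiotic use removes a patient under item 4, so that endpoint 6 erases its own events. The readable prohibited list does not name systemic antibiotics, so this is not shown.

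Some loss is already mitigated. Adverse event outcomes are collected and may capture some item 5 events, partial data stay in the Full Analysis Set, and footnote 8 keeps a patient in the per protocol analysis when recovery time can still be determined. None of this supplies diary or Day 14 data after exit.

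**Conclusion.** The point holds as a gap in the supplied text: followed as naturally read, the list and schedule give up outcome data that consenting patients could still provide, and analysis cannot restore them. It matters most for items 4 and 5, where leaving is plausibly outcome-related; for item 3 it is mostly the Day 14 contact.

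The size is modest and rests on an assumed 5–10% withdrawal: roughly 2–5 PCR-confirmed patients per arm without a resolution time, or up to 3.3–6.6 with early exit, and a complete-case bias small against 0.71 day. Bias under a censored time-to-event analysis was not estimated. The effect on endpoint 6 depends on an assumed relative risk and on how leavers are counted. The change should be made because it is cheap and prevents avoidable missing data; the primary comparison is not shown to be in danger.

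**What to change.** - State separately what ends study treatment and what ends follow-up. The treatment-stopping rules themselves stay unchanged.
- After items 3–5, for every randomised patient who has not withdrawn consent, continue the diary to its planned end and make the Day 14 call.
- Record an off-window visit as a protocol deviation, as the per protocol list already does, and not as a reason to end data collection.
- Analyse these data in the Full Analysis Set.

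The planned diary end needs stating for this to work, although it is a separate point that affects all patients: the observation period gives "follow-up – up to 2 days" after treatment, while the schedule marks the row "Patient Diary" at Visit 4 as well.

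The cost is protocol wording, continued use of a diary already issued and one call already planned, for about 120 × 0.05 to 0.10 = 6–12 patients per arm. The downside is minor site effort and some off-treatment data in the Full Analysis Set.

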- 3) lack of any data about the patient after administration of the study drug.

This sample, the most consistent with the “Intention-to-treat” principle, will be used for the ***Intention-to-treat analysis (ITT analysis)*** of the study therapy efficacy.

⁷ Licensee: OOO "NPF "Materia Medica Holding", No. 70100045

Per protocol set. This sample includes all patients who have received the complex therapy under the Protocol and completed all the scheduled visits. This sample will be used for the ***Per Protocol analysis (PP- analysis)*** of the study therapy efficacy. The list of deviations that may result in complete or partial invalidity of data is developed by a medical expert jointly with a biostatistician according to the study design:

1. The protocol deviations potentially resulting in partial or complete invalidation of the study patient's data: Violation of visit schedule.
2. Inappropriate distribution/supply of the study drug.
3. Prescription of prohibited therapy.
4. $\geq 25\%$ increase or reduction in the amount of the study therapy administered.
5. Inability to assess the patient's compliance using the formula (e.g. loss of pack with the product).
6. Major discrepancies between source documents and CRF detected during monitoring or another authorized check.
7. Violation of the procedure of obtaining informed consent.
8. Non-compliance with the clinical study protocol procedures.
9. Inability to collect all the patient's data used for evaluation of the study endpoints ⁸(e.g. lack of entries in source documents required for verification of inclusion/exclusion criteria, safety and efficacy criteria).
10. Any other protocol deviations covered by the term “major deviation”.

Evaluation of sample size

The sample size was assessed on the basis of the following rules and assumptions:

1. Statistical provisions.
 - 1.1 the power of the statistical tests “ $P = (1 - \beta)$ ” is assumed to be 80% (the probability of correct rejection of the null hypothesis is 0.8);
 - 1.2 the probability of a type I error “ α ” is allowed to be less than 5% (the probability of the erroneous acceptance of an alternative hypothesis is less than 0.05);
 - 1.3 the statistical criteria used are 2-sided;
 - 1.4 the protocol contains evaluation of minimum detectable effect at fixed: sample size, population variance, type 1 and 2 error values;
 - 1.5 the ratio between the sample sizes of the study drug and placebo groups is 1:1 (1 study drug patient - 1 placebo patient);

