⁸ If, considering the lack of some data in primary endpoint variable, the fact of reaching the primary endpoint by the patient can still be determined, the patient will be eligible for PP analysis (e.g. the diary lacks some records but the time of recovery can still be determined).

1.6 statistical hypotheses: null and alternative hypotheses about the superiority of the study drug over placebo using the applied dosing regimen:

$$H_0: M_1 - M_2 = 0$$

$$H_a: M_1 - M_2 \neq 0$$

where M_1 – the mean time to resolution of all symptoms in the study drug group;

M_2 – the mean time to resolution of all symptoms in the placebo group.

Analysis of the expected effect within the fixed sample will be carried out in accordance with the following formulas:

$$n_1 = kn_2$$

$$\varepsilon = \left(\frac{(z_{\alpha/2} + z_{\beta})^2 * (1 + 1/k) * \sigma^2}{n_2} \right)^{\frac{1}{2}}$$

where n_1, n_2 – the sample size of the study drug and the placebo groups respectively;

$\varepsilon = M_1 - M_2$ – the minimum detectable difference in time in study drug and placebo groups;

k – the coefficient of study drug /placebo sample ratio ($k=1$);

σ – the standard deviation;

$z_{\alpha/2}$ – a tabulated two-tailed z-test for α ;

z_{β} – a tabulated one-tailed z-test for β .

1.7 effective sample size will be determined using the formula:

$$N_{PP} = N_T * (1 - C_w),$$

where N_T – the final sample size;

N_{PP} – the value calculated in section 1.6, i.e. the expected number of the patients completing the study per protocol;

C_w – withdrawal coefficient.

2. Assumptions about the expected effects of the clinical study: To evaluate the minimum detectable effect at fixed sample size a priori estimate of population parameters should be performed:

A priori estimates for tested parameter variables in the groups:

Primary endpoint (efficacy criterion):

[figure not shown]
Time to resolution of ARVI symptoms.

Study drug group:

Time to resolution of symptoms was estimated on the basis of the previous studies.

$$T_{tr} = (\langle \max(N(2.6, 1.77), N(5, 1.47)) \rangle)^{9,10}$$

Where $\langle \dots \rangle$ stands for averaging operation, $N(x, s)$ – normally distributed random variable with the mean x and standard deviation s . corresponds to the Gumbel type I distribution¹¹ for power analysis this empirical distribution is approximated by the normal distribution with characteristics $m=5.17$, $\sigma=1.38$.

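### Footnote 8 gives a patient with an incomplete diary a written route into the per-protocol set only through a demonstrable recovery; nothing equivalent is written for a patient with gaps and no recovery on record

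*Combined protocol and SAP*

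**What the plan says.** The base definition of the PP set, under Samples, reads: "This sample includes all patients who have received the complex therapy under the Protocol and completed all the scheduled visits". A list of deviations follows, introduced as "The list of deviations that may result in complete or partial invalidity of data". Item 9 of that list is "Inability to collect all the patient's data used for evaluation of the study endpoints".

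Footnote 8, attached to item 9, relaxes it. Where some primary-endpoint data are lacking but "the fact of reaching the primary endpoint by the patient can still be determined, the patient will be eligible for PP analysis". Its example is that "the diary lacks some records but the time of recovery can still be determined".

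The FAS is defined differently. The only missing-data ground for leaving it is "lack of any data about the patient after administration of the study drug". It is described as "This sample, the most consistent with the “Intention-to-treat” principle" and is also used for efficacy.

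Under Evaluation of sample size, item 1.7, the count that drives the trial size, N_PP, is "the expected number of the patients completing the study per protocol". The hypotheses in item 1.6 compare mean times to resolution. LIFETEST and PHREG are on the list of SAS procedures but are not assigned to the primary endpoint, and no censoring rule appears anywhere.

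**The concern.** Take two patients with gaps in the diary. For one, the remaining entries fix a recovery time, and footnote 8 makes that patient eligible. For the other, the entries show continuing illness up to the last evaluable one. That patient carries information too (no recovery up to that point), but footnote 8 does not mention the case, item 9 counts against the patient, and a comparison of means has no value to enter.

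If the text is applied that way, membership of an efficacy set depends partly on the endpoint. When one arm recovers more slowly, or has more diary gaps, it loses more patients, and those lost are the ones not yet recovered. The remaining recovery times are then too short in both arms, by different amounts. The trial is sized on this set. Footnote 12 builds the planned 50% loss from 10% screening failures and withdrawals and 44% of the remainder without PCR confirmation, with no separate allowance for diary exclusions.

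**Working it through.** **Inputs from the documents.** Drug-group mean 5.17 days and SD 1.38; N_PP = 120, so 60 per arm; two-sided alpha 0.05; power 80%; C_w = 0.5.

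**Assumptions (not in the documents).** Placebo mean 5.17 + 0.71 = 5.88, same SD. A share q of diaries stops for good at a time uniform between 5 and 7 days after enrollment, independently of recovery time. A patient with a stopped diary is kept only if recovery time T is no later than the stop.

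**1. The plan's own figures.** ε = √[(1.960 + 0.842)² × 2 × 1.38² / 60] = 0.706, stated as 0.71 day. 120 / (1 − 0.5) = 240. Footnote 12: 0.90 × 0.56 × 240 = 121. All reproduce.

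**2. The mechanism at a single stopping time of 6 days.** With b = (6 − μ)/1.38, the share kept is Φ(b) and the mean of those kept is μ − 1.38 φ(b)/Φ(b).

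- Drug: b = 0.601; share kept 0.726; mean 5.17 − 1.38 × 0.333/0.726 = 4.54.
- Placebo: b = 0.087; share kept 0.535; mean 5.88 − 1.38 × 0.397/0.535 = 4.85.

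Within this subgroup the difference is about 0.32 day instead of 0.71. This is not the trial-level effect, because patients with complete diaries all stay.

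**3. The whole PP set.** Simulation of 4 million patients per arm gives the kept shares r, the means and the SDs s. Then SE = √[s_d²/(60 r_d) + s_p²/(60 r_p)] and power ≈ Φ(Δ/SE − 1.96).

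Worked case, 30% in each arm: r = 0.913 and 0.859; s = 1.337 and 1.362; SE = 0.262; Δ = 0.676; power = Φ(2.58 − 1.96) = 73%.

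| Stopped diaries, drug / placebo | True difference (days) | PP difference (days) | Power or two-sided error |
|---|---|---|---|
| 0 / 0 | 0.71 | 0.71 | 80% |
| 10% / 10% | 0.71 | 0.70 | about 78.5% |
| 30% / 30% | 0.71 | 0.68 | 73% |
| 10% / 30% | 0.71 | 0.58 | 60% |
| 30% / 10% | 0.71 | 0.80 | inflated difference |
| equal | 0 | 0 | 5.0% |
| 30% / 10% | 0 | 0.10 in favour of drug | 6.7% |

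The last row uses a common mean of 5.17; at a common mean of 5.88 it is 0.12 day and about 7.6%. Reversing the two rates reverses the sign.

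**4. Sensitivity to when diaries stop.** If stops are spread evenly over Days 1–8 with 20% in each arm, the difference stays at 0.71 and power falls to 75%, purely from lost patients. If instead incomplete-diary patients who recover after Day 7 are dropped, 10% in each arm gives 0.69 day and 79%, and 30% gives 0.66 day and 75%.

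**The case against.** The strongest reply is that the text does not order any exclusion. Footnote 8 states a sufficient condition (if, not only if), and the list covers deviations that may invalidate data, which leaves room for case review. The footnote can also be read as evaluability: a patient is eligible when it can be established whether the endpoint was reached. Both readings are open. But the footnote's example is a determinable time of recovery, and nothing is written for the patient who has not recovered. A set definition with two readings should be settled before unblinding.

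A reader might infer that slow recoverers are removed from the PP set. The documents do not support that. Anyone with a complete diary stays, however late the recovery, and so does a late recoverer with gaps whose recovery time can be determined. Nor does the difficulty fall only on slow recoverers. Resolution requires no further temperature increase during the observation period, so a diary that stops soon after an early recovery may also leave the endpoint undetermined. The PP set further requires all scheduled visits, including Visit 3 at Day 7±1. The simulated rule ignores both conditions and is a simplification.

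The FAS efficacy analysis is not subject to footnote 8. That stands and limits the consequence. It does not remove it: the documents do not say which set is primary. Sizing on N_PP is a planning step and does not itself make PP primary.

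**Conclusion.** The point holds as a gap in the set definition. Read literally with item 9, footnote 8 lets PP eligibility depend on whether recovery can be shown, and no alternative route or censoring rule covers the rest.

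A reader might go further and conclude that the drug–placebo comparison is distorted. That is not shown. The documents give no incomplete-diary rate, so both size and direction are unknown. At 10% in each arm the effect is small (0.70 day, about 78.5% power). It becomes material only at high or unequal rates (0.68 day and 73%; 0.58 day and 60%). Equal rates give no bias when there is no drug effect; with a true effect they attenuated the difference when diaries stopped at 5–7 days. A false advantage (about 0.10 day, 6.7% error) needs more gaps on drug than on placebo, and the documents offer no reason to expect that.

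These figures rest on the plan's normal approximation, the assumed placebo mean of 5.88 and the assumed stopping times. The change is worth making because it is cheap and removes discretion over who is counted; confidence that the effect would be material is moderate at most.

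**What to change.** Replace footnote 8 with:

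> A patient is not excluded from the PP set because of an incomplete diary, whether or not recovery was reached. Recovery time is used if determinable; otherwise the patient is censored at the last evaluable diary entry.

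State that the PP analysis of the primary endpoint uses LIFETEST/PHREG, which are already listed. The statistical hypotheses, now written as a difference in means, would need matching wording for that analysis.

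The cost is one sentence in the set definition and one in the analysis text. The downside is small: some PP patients contribute censored times, and censoring assumes that diary gaps are non-informative. Reporting the number of incomplete diaries by arm would let readers judge that assumption.
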